Try to anticipate all reasonably foreseeable sharing so that the consent document can also reflect that information. However, it is acceptable to amend this page later and explain either how re-consent of previously and currently enrolled participants will occur or why re-consent should not be required.

The IRB reviews this page against the consent document (if one exists) to demonstrate the ethical principle of Respect for Persons by confirming that plans for sharing do not go against what participants would understand about the use of their data/specimens.

The IRB also ensures there are adequate protections for the privacy of participants and the confidentiality of participants' data/specimens when data is shared with others.

1. * Is it likely investigators could discover information about child/elder abuse or neglect that would require mandatory reporting by the investigators or staff?

The Code of Virginia requires that most medical personnel and all employees of institutions of higher education report suspected child/elder abuse or neglect.

Yes
 No

2. * Is it likely investigators could discover a previously unknown reportable disease or condition that would require mandatory reporting by the investigators or staff (i.e., HIV, coronavirus, hepatitis, etc.)?

Yes No

3. * Will the sponsor or investigator obtain a Certificate of Confidentiality for this study?

Certificates of Confidentiality (CoC) are issued by the National Institutes of Health (NIH), the FDA and CDC to protect identifiable research information from forced disclosure. All human subject research studies regardless of funding can qualify to receive a CoC. A CoC is automatically issued for research that was ongoing on December 13, 2016. or initiated after that date. For more information, see <https://humansubjects.nih.gov/coc/>

No - Will not obtain CoC for this study
 Yes - CoC has been obtained or issued automatically
 Yes - CoC request is pending
 Yes - Plan to submit request for CoC and will amend study/ICF once status of request is known

4. * Select the way(s) that individual-level information or biospecimens (including DNA) may be used by the VCU PI or VCU study team for other future research projects (i.e. analyses beyond/apart from the aims of this study)?

See *help text for definitions*.

Will use directly identifiable information or specimens.
(‘Directly identifiable’ means that identifiers like name, medical record number, social security number, etc. are included in/attached to the dataset/specimens. Maintaining identifiable data for future research is treated as a registry by the VCU IRB. The IRB must approve the new research use in an amendment to this study or as part of a new study before the project is initiated. You will be asked more questions about this on a later page)

Will use de-identified or indirectly identifiable information or specimens.
(‘De-identified’ means that a linkage/key code exists that links identifiers to data/specimens. When the researcher holds both the data and the key, the VCU IRB considers the subjects to be readily identifiable.
Maintaining identifiable data for future research uses is treated by the IRB as a registry. The IRB must approve the new research use in an amendment to this study or as part of a new study before the project is initiated. You will be asked more questions about this on a later page)

Will use anonymized information or specimens.
(‘Anonymized’ means that 1) no linkage/key codes exist that link identifiers to data/specimens; and 2) subjects cannot be readily identified, i.e. no direct or indirect identifiers or identifiable combinations of variables. The VCU IRB considers uses of anonymized data/specimens to not be human subject research.)

Will use aggregate results (summary-level results), not individual-level information or specimens.
(The VCU IRB considers uses of aggregate data to not be human subject research because there are no individual subjects.)

Will contribute to an existing registry or repository
(You will be asked more questions about this on a later page.)

Will not use information/specimens for purposes beyond this study.

Not sure and will submit an amendment when known

Other use(s) of individual-level information in a way not listed above

5. * Select the way(s) the VCU PI/study team may share individual-level information or biospecimens (including DNA) with other researchers who are not on this study team (i.e. for analyses beyond/apart from the aims of this study).

See [help text for definitions](#).

Will share directly identifiable information or specimens with other researchers.
(‘Directly identifiable’ means that identifiers like name, medical record number, social security number, etc. are included in/attached to the dataset/specimens. Maintaining identifiable data for future research uses is treated by the VCU IRB as a registry. The data recipient’s use of identifiable data would require them to obtain IRB review. You will be asked more questions about this on a later page.)

Will share de-identified or indirectly identifiable information or specimens with other researchers.
(‘De-identified’ means that a linkage/key code exists that links identifiers to data/specimens. The VCU researcher maintains the key but does not share it with any other researchers. The recipient’s use of de-identified data/specimens may not be human subject research if there is documentation that the key will never be shared with the recipient, but they should check with their own IRB about review requirements. You will be asked more questions about this on a later page.)

Will share anonymized information or specimens with other researchers.
(‘Anonymized’ means that 1) no linkage/key codes exist that link identifiers to data/specimens; and 2) subjects cannot be readily identified (i.e. no direct or indirect identifiers or identifiable combinations of variables). The VCU IRB considers uses of anonymized data/specimens by other researchers to not be human subject research, but the recipient should check with their own IRB about review requirements.)

Will only share aggregate results (summary-level results), not individual-level information or specimens.
(The VCU IRB considers uses of aggregate data to not be human subject research because there are no individual subjects. The data recipient should check with their own IRB about review requirements.)

Will contribute to an existing registry or repository (You will be asked more questions about this on a later page.)

Will submit data to an NIH genomic data repository (You will be asked more questions about this on a later page.)

Will not share information/specimens with other researchers.

Not sure and will submit an amendment when known

Other sharing of individual-level information with other researchers

6. * The Principal Investigator certifies that after the study has been closed with the VCU IRB, the following conditions will be met whenever individual level research information and/or specimens are used or shared:

- The identities of participants who are represented in the dataset/specimens will not be readily ascertainable or otherwise re-identifiable by the recipient;
- If a linkage/code key is created, it will be maintained at VCU and not shared with the recipient under any circumstances;
- The PI will have no knowledge that the remaining information could be used alone or in combination with any other information to identify the individuals represented in the data; and
- The PI agrees to abide by this sharing plan even after the study has been closed with the VCU IRB.

Yes

No

N/A - No sharing will occur

7. If the Certificate of Confidentiality has been obtained by the PI, upload it here:

Pertinent and Incidental Findings

1. * Is it likely investigators could discover a participant's previously unknown condition (e.g. pregnancy, disease, suicidal thoughts, wrong paternity, genetic results, or other findings that may be of importance to health or well-being) or if a participant is engaging in illegal or reportable activities:

- Yes
- No

2. * Describe what possible pertinent or incidental findings stemming from research-only procedures may be discovered.

It is possible that participants may disclose the use of illegal substances and/or underage drinking.

3. * Explain what actions or procedures research personnel should take to inform the PI of such a discovery :
Research personnel will not take any action if participants disclose the use of illegal substances or underage drinking. One aim of this study is to understand the impact of our newly developed innovative prevention intervention, the Personalized Feedback Program (PFP) on substance use among college students. Thus, the nature of the study requires that we ask participants about their current and past substance use. Participants will be encouraged to reach out to their university counseling/health services if they experience distress during the study.

4. * Will findings be disclosed to participants and/or any other person/group outside of the study team?

- Yes
- No

5. If pertinent and/or incidental findings will not be disclosed, explain why not:

One aim of this study is to preliminarily evaluate the efficacy of the Personalized Feedback Program (PFP) in reducing risky substance use among college students as compared to an assessment only control group, a computer-delivered intervention based on brief motivational intervention (BMI) content/principles, and a combined PFP+BMI condition. Thus, the nature of the study requires that we ask participants about their current and past substance use. If we were to share any incidental findings, this could jeopardize the comfort and safety of potential participants to answer the survey honestly.

Risk Benefit Complete

Protocol Progress:

- ➊ INITIAL SETUP
- ➋ BACKGROUND, RATIONALE & GOALS

- ④ RESEARCH PLAN
- ⑤ CONSENT PLAN
- ⑥ RISKS, PRIVACY & CONFIDENTIALITY
- ⑥ POPULATIONS WITH SPECIAL CONSIDERATIONS
- ⑦ INSTITUTIONAL REQUIREMENTS
- ⑧ DOCUMENTS

Click Continue below to go to the next section

View: SF2 - Populations with Special Considerations

Populations with Special Considerations

1. * Check all participant groups that will be either
 - a) Specifically included in this study or
 - b) Discernable in the research data/specimens.

(Selections will branch)

- Children
- Emancipated minors
- Wards of the State
- Pregnant women or fetuses
- Neonates or Post-delivery Materials
- Prisoners
- Decisionally Impaired Adults
- VCU / VCUHS students or trainees
- VCU / VCU Health System employees
- Individuals with limited English proficiency
- Active military personnel
- Student populations in K-12 educational settings or other learning environments
- Members of a federally recognized American Indian and Alaska Native tribe

None of the Above

2. Additional considerations for student populations:

* Select all who will be research participants in the study:

VCU Students

K-12 Students

Parents/Guardians of Students

Teachers

Administrators

Other

3. If applicable, describe any alternative activities for students (including VCU students) who choose not to participate in the research.

4. * Describe how the study will minimize the possibility of coercion to participate.

We prevent undue coercion to participate by providing participants with the opportunity to decline participating in the study even after they initiate the consent process. Recruitment will only be done electronically, thereby further reducing participants' chances of feeling coerced. In addition, participants will have the opportunity to seek additional information about participating in the study. In the electronic consent document the decision to consent or to decline consent is presented at the end of the consent document with the following statement: "I have been provided with an opportunity to read the consent form carefully. All of the questions that I wish to raise concerning this study have been answered. Do you consent to participate in this research study? 'Yes' or 'No'." In addition, the consent document will be available and individuals will be encouraged to download a copy for their own records. The study email will be available in the consent document. Individuals who are uncertain about whether they want to participate will therefore have the opportunity to contact the coordinator with questions about the study.

View: SF2 - Populations with Special Considerations Section Complete

Populations with Special Considerations Section Complete

Protocol Progress:

① INITIAL SETUP

② BACKGROUND, RATIONALE & GOALS

③ RESEARCH PLAN

④ CONSENT PLAN

⑤ RISKS, PRIVACY & CONFIDENTIALITY

⑥ POPULATIONS WITH SPECIAL CONSIDERATIONS

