4. * Describe the study procedures/methods for identifying and recruiting participants. Address the following three aspects of recruitment in your response.

1. Identification of potentially eligible participants or secondary data/specimens of interest.

- What database(s) will be queried to identify secondary data/specimens
- How potential participants' contact information will be obtained

2. Recruitment procedures to invite participation in the study (when applicable):

- How each of the written or verbal recruitment materials and reminders (selected above) will be used
- Who will contact or respond to potential participants
- Locations where recruitment procedures will take place
- The timing and frequency of recruitment attempts

3. Eligibility screening prior to consent and how those activities will be carried out (when applicable)

See the help text for additional guidance.

Participants will be identified by self-selection during the Spit for Science baseline survey being conducted in the Fall 2021 semester. As part of the baseline survey, participants will be asked a yes/no question about their interest in learning more about the current spin-off study. Participants are informed that if they indicate 'yes' that their data and contact information will be shared with the Personalized Feedback Programs for College Students study (see document named: Spin-Off Invitation through S4S Baseline Survey). Spit for Science assigns randomly generated coded spin-off IDs for each participant. For participants that indicate 'yes' to the spin-off study interest question asked within the Spit for Science baseline survey, this spin-off ID is provided to the study project coordinator as part of the 'turnover' data, which includes email addresses, permanent address, phone number(s) and text permission if provided. The information will also include responses to the baseline measures. This data sharing will occur through a VCU approved file sharing application (like REDCap Send-It), a conditional Data Access Group (DAG) in the S4S baseline REDCap Project and/or through a shared, 'user-assigned' Participant Tracking REDCap Project.

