When participants enter our study consent, they will be asked to provide their VCU email address, which will be used to match the participant back to the information provided by Spit for Science, including the spinoff ID. The spin-off ID will then be used throughout the course of the study procedures to link survey record IDs, survey data, and study data. Should they participate in the study, all survey data will be kept separate from identifiable information. The connection between a student email address and a particular record ID number is maintained behind the scenes in the REDCap system and on a password-protected secure server accessible only to select study staff. This key will be kept indefinitely on a secure server. All identifiable information from students who participate in the study will be deleted at the end of the study.

Once the study team receives the list of potential participants, the study team will randomize the participants across the four conditions. All participants have an equal chance of being randomized into each of the four conditions. The study team will then send these potential participants the "Study Enrollment Email." This email will contain further details about the study along with a link to this study's consent in REDCap. They will be asked to enter their VCU email address as part of the consent process. Once they consent to participate, they will be automatically redirected to their condition's program. These programs are outlined in the Study Procedures section. At the conclusion of their participation in their condition, additional contact information may be requested. Specifically, participants will be asked to confirm their VCU email address and phone number where they can be contacted to participate in the follow-up assessments. Additionally, if information that allows the study to carry out compensation steps was not provided previously (e.g. the participant's permanent address) it will be requested at this time. While the email and mailing address questions will be required, students are able to decline to share their phone number.

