The study survey will have a response limit of 400 respondents. Participants will be invited on a rolling basis (in batches according to when they complete the baseline survey) until we have reached 400. Once 400 participants have completed participation, the baseline survey will provide a message to subsequent interested participants indicating that: "Thank you for your interest in the personalized feedback program. This study is currently full. If the study opens enrollment in the future, we may contact you at that time to see if you are still interested. In the meantime, please keep an eye out for more emails from Spit for Science with other opportunities to participate in research!" The study staff will inform Spit for Science once the response limit is approaching/met and Spit for Science will remove (or alter the information presented indicating study enrollment is full) in the baseline survey to help ensure that unnecessary ascertainment and data sharing is avoided.

Starting one week after the initial invitation email is sent, eligible students who have not yet enrolled in the RCT will be sent email or text (if permission given) reminders. Reminders will be sent weekly for three weeks or until we have achieved our desired N.

All participants will be invited to complete follow-up assessments at two timepoints: 30 days after their initial participation (T2) and 3 months after their initial participation (T3). At each timepoint, they will be contacted by the study coordinator via the email address they provided on the initial survey (for content see "Intro Email/Reminder T2" and "Intro Email/Reminder T3"). The emails will contain a link to the T2 Survey and T3 Survey respectively. The reminder schedule will mirror the reminders for initial entry into the study. That is, starting one week after the invitation

email is sent, participants who have not yet completed the T2 (and later T3) survey will be sent email reminders. In addition to emails, students who shared their phone numbers in the initial survey at T1 will receive reminders via text. Reminders will be sent weekly for three weeks for each survey (for content see "Text Reminders").

5. * Does this study have a separate protocol document (i.e. a multisite or sponsor's protocol) that contains a detailed description of the study's methodology?

Yes

No

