
Group	Types Waivers	Roles	Roles - Other	Electronic Signatures	Consent	Coercion	Decision	Re- Consent	
					window, and and return to open it again the at any time document to prior to their provide their participation. consent or Participants not. will not be able to participate in any of the programs or answer any survey items without giving consent to participate in the study. If participants do not consent to participate after reading the consent, they will not be contacted about the study again. Once participants do consent to participate in the study, they will be automatically taken to the program to which they have been randomized followed by the brief set of follow-up questions (Post-Program Survey).				

2. Upload any consent / assent documents:

View: SF2- Waiver of Documentation of Consent

Waiver of Documentation of Consent

Consent groups that require a waiver of documentation (i.e. consent form not signed):

Group	Types	Waivers	Roles	Roles - Consent Other	Decision	Status Change
All participants the above (select waiver documentation of below)	None of the forms (waiver of documentation of consent)	Waiver of Signature Requesting Consent/Permission	N/A: Consent	In the baseline Spit for Science Survey delivered in the Fall semester of 2021, participants will be asked if they are interested in participating in our study. Those who say "Yes" to the interested question will be asked if their information can be shared with our study. Those who say "Yes" to the data sharing question will receive the "Study Enrollment Email" from our study coordinator. This email contains a link to the Study Consent document. Participants are able to review the consent, close the window, and open it again at any time prior to their participation. Participants will not be able to participate in any of the programs or answer any survey items without giving consent to participate in the study. If participants do not consent to participate after reading the consent, they will not be contacted about the study again. Once participants do consent to participate in the study, they will be automatically taken to the program to which they have been randomized followed by the brief set of follow-up questions (Post-Program Survey).	The study consent process is conducted on-line, meaning participants can take as much time as they need to make a decision.	

1. * Select which of the following applies to the consent groups used in this study:

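### The study team assigns arms before consent, so students who decline or ignore the invitation are lost after randomisation without outcomes, and nothing described hides the assignment from those who invite and remind

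*Protocol*

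**What the plan says.** Study Procedures, question 4 (identifying and recruiting participants), gives this sequence:

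1. Students who answer yes to the interest question in the baseline survey are passed to the project coordinator with their contact details. On the same transfer: "The information will also include responses to the baseline measures".
2. "Once the study team receives the list of potential participants, the study team will randomize the participants across the four conditions". The ratio is equal: "All participants have an equal chance of being randomized into each of the four conditions".
3. The study team then emails the enrolment invitation with the consent link. Students who have not enrolled get weekly email or text reminders for three weeks, or until the target number is reached.
4. "Participants will be invited on a rolling basis (in batches according to when they complete the baseline survey) until we have reached 400".
5. "Once they consent to participate, they will be automatically redirected to their condition's program".

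Question 6 of the same section (design and procedure) also puts assignment first: the first 400 students to answer yes are randomised, and invitations from the study coordinator follow. There, follow-up at 30 days and 3 months goes to enrolled participants only.

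The Consent Process section adds that no program or survey item is open to a student who has not consented, and: "If participants do not consent to participate after reading the consent, they will not be contacted about the study again".

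**The concern.** When assignment comes before consent, the randomised set and the set that can give outcomes differ from the start. A student who is assigned and never consents cannot be followed, so an outcome comparison of everyone randomised cannot be made. What remains is a comparison of those who consented, which is protected by randomisation only if enrolment is unrelated to arm.

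That condition would hold most securely if nobody who could influence enrolment knew the arm. Here the study team creates the assignments, sends the invitations and sends the reminders, and its coordinator also has the students' baseline answers. The protocol describes no independent generation of the sequence, no masking of the person sending reminders and no other form of concealment. Anyone who knew the arm and the baseline answers could chase some students harder than others.

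This is a matter of trial conduct. A statistical analysis plan cannot repair it, because outcomes that were never collected cannot be recovered in analysis.

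**Working it through.** **Order of events.** The two descriptions in Study Procedures disagree on what 400 counts but agree on the order.

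| | Question 4 | Question 6 |
|---|---|---|
| Who is assigned | everyone on the list received, in batches | the first 400 to answer yes |
| What 400 counts | respondents or completers ("Once 400 participants have completed participation, the baseline survey will provide a message to subsequent interested participants") | students assigned |
| Assignment relative to consent | before | before |
| Arm first used | redirect after consent | redirect after consent |

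Reconciling the two counts would not change the point. Under either, a student who does not consent has been randomised and has no outcomes.

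**The plan's own figures.** Study Population, question 3, gives 4 arms of 100 and a target of 300 at each stage.

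- 4 × 100 = 400.
- Implied allowance: (400 − 300)/400 = 25%.
- Check: 300/(1 − 0.25) = 400. The figure reproduces.

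Study Population attributes this margin to future attrition, while question 6 of Study Procedures links the target of 300 to earlier enrolment rates. One 25% margin therefore has to cover both non-enrolment and later dropout, and the documents do not split it.

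**Range of the pre-consent loss.** The consent rate c among assigned students is not stated; the values below are assumptions.

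- If 400 are assigned (question 6): never enrolled = 400 × (1 − c). Retention needed to reach 300 = 300/(400 × c).
- If invitations continue until 400 respond (question 4): assigned = 400/c, rounded up. Never enrolled = that number − 400.

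| c (assumed) | Never enrolled, 400 assigned | Retention then needed for 300 | Assigned to reach 400 | Never enrolled |
|---|---|---|---|---|
| 0.9 | 40 | 300/360 = 83% | 445 | 45 |
| 0.8 | 80 | 300/320 = 94% | 500 | 100 |
| 0.7 | 120 | 300/280 > 100%, impossible | 572 | 172 |
| 0.5 | 200 | 300/200 > 100%, impossible | 800 | 400 |

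If 400 are assigned, 300 is out of reach once c falls below 300/400 = 0.75.

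**With assignment at consent.** 400 randomised = 400 consented, so the loss between randomisation and consent is 0. The whole 25% is then available for true attrition: 400 × 0.75 = 300, or 75 per arm.

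**The case against.** The strongest reply is that the loss need not bias anything. One enrolment email and one study consent are described, neither as arm-specific, and the arm first appears at the redirect. A student who declines has no described way of knowing the arm, so non-consent may be unrelated to it, and the consenting students would then still form a fair randomised comparison. This stands. It is why the point is a risk to remove and not a demonstrated bias.

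Staff discretion also looks limited. Entry is by the student's own yes. Data Retention, question 2, says participation in the baseline survey is the only eligibility requirement, and reminders follow a fixed weekly schedule. Active Internet Data Collection, question 2, says investigators never see identifiable data. That assurance does not reach the coordinator, who receives contact details together with baseline responses. The gap left is undocumented masking. A reader might infer that whoever sends reminders sees each student's arm and drinking history, but the protocol does not say so.

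Three other stronger readings also go beyond the documents:

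- **That non-enrolled students have no data.** They have baseline responses and lack outcomes, so enrolled and non-enrolled students could be compared at baseline by arm.
- **That 25% of assigned students are lost this way.** The 25% mixes non-consent with later dropout, which would remain after the change.
- **That later batches replace those who decline.** This fits the count in question 4 only; question 6 taken alone implies no replacement.

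The bar on further contact covers those who decline after reading the consent. Those who ignore the email are still reminded, but without consent they too give no outcomes.

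**Conclusion.** The point holds as a weakness of the stated procedure. The protocol puts assignment by the study team before consent in both places where it describes assignment. Loss after randomisation without outcomes is therefore built in, and no concealment from those who invite and remind is described. Bias is possible, chiefly through selective chasing, and is not shown.

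The size cannot be derived from the documents. Under assumed consent of 50% to 90%, the number randomised without outcomes is 40 to 200 if 400 are assigned and 45 to 400 if invitations run until 400 respond. The conclusion rests on the stated order of events and on the absence of any described safeguard, not on these ranges. Early assignment also gains nothing, since the arm is not needed until the redirect. The change is worth making before invitations go out, because it cannot be made for students already assigned.

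**What to change.** Replace the assignment sentences in Study Procedures, questions 4 and 6, with text such as:

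> The allocation sequence is generated in advance in a 1:1:1:1 ratio and loaded into REDCap. A student's assignment is revealed automatically only on acceptance of the consent. Study staff cannot see it before then.

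Invitations and reminders then go to unassigned students, every randomised student is a consented one, and the all-randomised comparison starts at consent. In the same amendment, make questions 4 and 6 agree on what 400 counts; with this change it can be consented and randomised students.

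**Cost.** A small set-up task before launch and a short amendment, with no extra participants. REDCap already hosts the consent and the redirect. The protocol does not describe its randomisation function, so the study team should confirm that the set-up is available.

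**What it does not address.** Dropout after the redirect remains. It may differ by arm, because the expected T1 time runs from about 10 minutes for control to 40–50 minutes for PFP+BMI.
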